7.0 Study Objectives

Note (*): While the protocol's primary and secondary objectives as written do not explicitly differentiate between ChAdOx1-HBV plus MVA-HBV vaccines with and without nivolumab (i.e., Group 3 and Group 4), the intent was to evaluate the safety, reactogenicity, and immunogenicity for each treatment group. Therefore, this SAP has been developed to evaluate each group's effect on these objectives.

Note (**): While the protocol's secondary objective as written does not explicitly reference the MVA-HBV-only group (i.e., Group 1), the intent was to evaluate each treatment group's effect on Hepatitis B markers. Therefore, this SAP has been developed to evaluate each group's effect on these markers.

7.1 Primary Objectives

- Determine the safety and reactogenicity of the following in participants with Chronic Hepatitis B Virus (CHB) infection and virally suppressed with oral antiviral medication:
 - MVA-HBV vaccine

- ChAdOx1-HBV plus MVA-HBV vaccines
- ChAdOx1-HBV plus MVA-HBV vaccines and nivolumab*

7.2 Secondary Objectives

- Determine the immunogenicity of the following in participants with CHB infection and virally suppressed with oral antiviral medication:
 - MVA-HBV vaccine
 - ChAdOx1-HBV plus MVA-HBV vaccines
 - ChAdOx1-HBV plus MVA-HBV vaccines administered with nivolumab*
- Determine the impact of PD-1 blockade timing relative to vaccination on immunogenicity in participants with CHB infection and virally suppressed with oral antiviral medication
- Determine the effect of the following on the level of hepatitis B markers**:

- ChAdOx1-HBV plus MVA-HBV vaccines without nivolumab
- ChAdOx1-HBV plus MVA-HBV vaccines with nivolumab

7.3 Exploratory Objectives

- Assess the HBV-specific cellular immune response generated by ChAdOx1-HBV plus MVA-HBV vaccines
- Determine the effect of ChAdOx1-HBV plus MVA-HBV on hepatitis B biomarkers

8.0 Study Design

This is a Phase 1b/2a, multicentre study of ChAdOx1-HBV and MVA-HBV vaccines (VTP-300). The study is planned to be conducted at up to 14 centres in 64 participants chronically infected with Hepatitis B Infection and virally suppressed with approved oral anti-HBV therapies. This is an open-label study comparing the safety, tolerability and immunogenicity of MVA-HBV alone, ChAdOx1-HBV followed by MVA-HBV, and ChAdOx1-HBV plus MVA-HBV vaccines with or without the anti-PD-1 antibody, nivolumab.

The overall duration of the study is estimated to be approximately 17 months from study initiation (first participants in) to study completion. The individual participants' participation is approximately 10.5 months from enrolment to study completion unless prematurely discontinued. The study consists of a 42-day screening period, a study period of 9 months, and an end of study visit.

All treatment groups will receive study vaccine regimen on Day 0 and Day 28. In addition, participants will be asked to return to the study site at Day 7, Day 35, Month 3, Month 6, and Month 9. Participants will also be contacted by phone on Day 1 and Day 29. Some participants may receive an additional MVA-HBV boost at Month 3 and will be contacted by phone the day after this booster dose at Month 3 + 1 day and attend a further clinic visit on Month 3 + 7 days, if it occurs.

Solicited adverse events will be captured from 0 to 7 days post-vaccinations. Immunogenicity and safety assessments including unsolicited adverse events, laboratory tests, vital signs, and physical examinations will be assessed until the end of study (Month 9).

Participants will be randomised to all open groups in a 1:1:1:1 allocation as each group is initiated. In Group 1, MVA-HBV participant safety data will be evaluated 7 days after the first dose of study vaccine in the first 6 participants prior to initiation of the prime-boost regimen of ChAdOx1-HBV followed by MVA-HBV (Group 2). Participants in Groups 3 and 4 will be dosed in parallel to receive ChAdOx1-HBV (with and without nivolumab) on Day 0 followed by MVA-HBV with nivolumab on Day 28. Groups 3 and 4 will be initiated after evaluation of safety data 7 days after the first 6 participants in Group 2 have received ChAdOx1-HBV.

The overall study design is displayed in Figure 1 below.

[figure not shown]

Figure 1 Overall Study Design

An interim safety and immunogenicity look will be performed to evaluate immunogenicity and safety data from all participants up to the cut-off date.

8.1 Sample Size Considerations

The sample size of 16 participants per treatment group was originally chosen to assess the variability in both immunologic responses, as well as the potential change in HBsAg. With 16 participants, the trial also has an 80% chance to detect any severe or serious adverse event that would occur at a 10% incidence.

Following the interim analysis, enrolment into Groups 1 and 4 ceased (with n=10 and 9, respectively), and enrolment continued for Groups 2 and 3 in a 1:1 randomisation allocation.

8.2 Randomisation

Participants will be randomised to all open treatment groups in a 1:1:1:1 allocation as each group is initiated.

Randomisation will be performed via the IXRS (Interactive Voice/Web Response System). At Day 0, eligible participants will be assigned to Group 1, Group 2, Group 3, or Group 4. Initially only Group 1 will be open and at least 6 participants will be randomised directly into this group. After the Safety Monitoring Committee (SMC) confirms that Group 2 can be initiated, at least 6 participants will be randomised directly into Group 2. Finally, once the SMC confirms that Groups 3 and 4 can be opened, participants will be randomised to all open treatment groups backfilling the randomisation scheme until 16 participants have been randomised to each treatment group.

Each participant will receive a unique randomisation number when he/she is assigned to the treatment group. Participants will be allocated to treatment groups according to the randomisation code.

9.0 Study Endpoints

9.1 Endpoints/Estimands

The below table links the endpoints to the study objectives.

Objectives	Endpoints/Estimands	Population
Primary		

Objectives	Endpoints/Estimands	Population

 • Determine the safety and reactogenicity of the following in participants with CHB infection and virally suppressed with oral antiviral medication: 
 – MVA-HBV vaccine – ChAdOx1-HBV plus MVA vaccines – ChAdOx1-HBV plus MVA vaccines and nivolumab 	
 • Safety and reactogenicity of the vaccine(s): incidence of adverse events (AEs), serious adverse events (SAEs), \geq Grade 3 study vaccine-related AEs within 4 weeks of vaccination • Safety of the vaccines with nivolumab: incidence of AEs, SAEs, \geq Grade 3 AEs within 4 weeks of dosing • Incidence of adverse events of special interest • Number and proportion of participants reporting treatment-emergent AEs within each treatment group • Number and proportion of participants within each treatment group with potentially clinically significant laboratory values and vital signs within each treatment group • Change from baseline in laboratory tests and vital sign measurements to each time point of collection 	Safety
Secondary 
 • Determine the immunogenicity of the following in participants with CHB infection and virally suppressed with oral antiviral medication: 
 – MVA-HBV vaccine – ChAdOx1-HBV plus MVA-HBV vaccines – ChAdOx1-HBV plus MVA-HBV vaccines administered with nivolumab • Determine the impact of PD-1 blockade timing relative to vaccination on immunogenicity in participants with CHB infection and virally suppressed with oral antiviral medication 	
 • Magnitude and avidity of HBV-specific CD4+ and CD8+ T cells induced by each regimen • Effect on the frequency and magnitude of HBV infection markers (HBsAg, Hepatitis B surface antibody seroconversion, hepatitis B DNA, HBeAg) 	
 • Immunogenicity (for ICS, ELISpot, and HBsAg analyses) • ITT (for HBsAg, HBeAg, HBV DNA, and seroconversion analyses)

Objectives	Endpoints/Estimands	Population

 Determine the effect of the following on the level of hepatitis B markers: 
 ChAdOx1-HBV plus MVA-HBV vaccines without nivolumab ChAdOx1-HBV plus MVA-HBV vaccines with nivolumab 		
Exploratory		

 Assess the HBV-specific cellular immune response generated by ChAdOx1-HBV plus MVA-HBV vaccines Determine the effect of ChAdOx1-HBV plus MVA-HBV on hepatitis B biomarkers 	
 Effect on hepatitis B core-related Ag (HBcrAg) Effect on hepatitis B pregenomic RNA (HBpgRNA) Induction of individual phenotypic subsets of CD4+ and CD8+ T cells induced by vaccination The T cell breadth of response to the HBV proteins encoded by the ChAdOx1-HBV plus MVA-HBV vaccines Frequency of regulatory T cells responses 	Immunogenicity

Note: This SAP only addresses primary, secondary, and select exploratory endpoints. All other exploratory endpoints to be analysed will be described in separate documentation.

9.2 Population Sets

9.2.1 Enrolled Participants

Enrolled participants are defined as participants who met all the eligibility criteria.

9.2.2 Intent-to-treat Analysis Set

The intent-to-treat analysis set is defined as all randomised participants. Participants will be presented according to the treatment group that they were randomised to. This will be the primary analysis set for all demography and HBsAg, HBeAg, seroconversion, and HBV DNA immunogenicity analyses.

9.2.3 Safety Analysis Set

The safety analysis set is defined as all participants who received at least one vaccination. Participants will be presented according to the vaccination regimen actually received as defined in Table 2. This will be the analysis set for all safety analyses.

9.2.4 Per-protocol Analysis Set

The per-protocol analysis set is defined as all participants in the intent-to-treat analysis set who received the correct study vaccine at both vaccinations and who had no major protocol deviations that could potentially bias trial analyses. Participants will be presented according to the treatment group they were randomised to.

9.2.5 Immunogenicity Analysis Set

The immunogenicity analysis set is defined as all participants in the per-protocol set who have available immunogenicity data to evaluate the immunogenicity endpoints and do not have any major protocol deviations that could impact on the results of the immunological analysis.

Immunology data from at least baseline and one post-baseline time point (for ICS and ELISpot) is required. Participants will be presented according to the treatment group that they were randomised to. This will be the analysis set for Intracellular Cytokine Staining (ICS) and Enzyme-linked Immunosorbent Spot (ELISpot) immunogenicity analyses.

10.0 Conventions and Derivations

10.1 Treatment Groups

In the outputs, the treatment groups will be labelled as Group 1, Group 2, Group 3 and Group 4, rather than the full description of the first and second vaccinations, in order to conserve space. The definitions of these 4 groups are described in Table 1.

Table 1 Treatment Groups

Treatment Group	1 st Vaccination	2 nd Vaccination
Group 1	MVA-HBV 1 x 10 ⁸ pfu	MVA-HBV 1 x 10 ⁸ pfu
Group 2	ChAdOx1-HBV 2.5 x 10 ¹⁰ vp	MVA-HBV 1 x 10 ⁸ pfu
Group 3	ChAdOx1-HBV 2.5 x 10 ¹⁰ vp	MVA-HBV 1 x 10 ⁸ pfu + Nivolumab 0.3 mg/kg
Group 4	ChAdOx1-HBV 2.5 x 10 ¹⁰ vp + Nivolumab 0.3 mg/kg	MVA-HBV 1 x 10 ⁸ pfu + Nivolumab 0.3 mg/kg

For the safety analysis, the actual treatment groupings are assigned as follows:

- Group 1 = MVA-HBV in 1st vaccination
- Group 2 = ChAdOx1-HBV in 1st vaccination, No Nivolumab in 2nd vaccination
- Group 3 = ChAdOx1-HBV in 1st vaccination, Nivolumab in 2nd vaccination
- Group 4 = ChAdOx1-HBV + Nivolumab in 1st vaccination

The possible combinations of treatments at the first and second vaccinations and the resulting actual treatment group are described in Table 2.

Table 2 Actual Treatment Groups

Randomisation	Actual 1 st Vaccination Given	Actual 2 nd Vaccination Given	Treatment Group Assigned for the Safety Analysis
Group 1	MVA-HBV	MVA-HBV	Group 1
Group 2	ChAdOx1-HBV	MVA-HBV	Group 2

Randomisation	Actual 1 st Vaccination Given	Actual 2 nd Vaccination Given	Treatment Group Assigned for the Safety Analysis
Group 3	ChAdOx1-HBV	MVA-HBV + Nivolumab	Group 3
Group 4	ChAdOx1-HBV + Nivolumab	MVA-HBV + Nivolumab	Group 4
Group 1	MVA-HBV	No vaccination given	Group 1
Group 2	ChAdOx1-HBV	No vaccination given	Group 2
Group 3	ChAdOx1-HBV	No vaccination given	Group 2
Group 4	ChAdOx1-HBV + Nivolumab	MVA-HBV (Nivolumab not given)	Group 4
Group 4	ChAdOx1-HBV + Nivolumab	No vaccination given	Group 4
Group 3	ChAdOx1-HBV	MVA-HBV (Nivolumab not given)	Group 2
Group 4	ChAdOx1-HBV (Nivolumab not given)	MVA-HBV + Nivolumab	Group 3
Group 4	ChAdOx1-HBV (Nivolumab not given)	MVA-HBV (Nivolumab not given)	Group 2
Group 4	ChAdOx1-HBV (Nivolumab not given)	No vaccination given	Group 2

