### ***3.1.4 Individual Stopping Rules (All Vaccinated Study Participants)***

In addition to the above stated group holding rules, stopping rules for individual participants will apply (i.e. in addition to withdrawal of individuals from a second vaccination). Study participants who present with at least one of the following stopping rules will be withdrawn from further vaccination in the study:

- **Local reactions:** injection site ulceration, abscess or necrosis
- **Laboratory AEs:**
  - The participant develops a Grade 3 laboratory adverse event considered possibly, probably or definitely related within 7 days after vaccination and persisting continuously at Grade 3 for >72 hours
- **Systemic solicited adverse events:**
  - The participant develops a Grade 3 systemic solicited adverse event considered possibly, probably or definitely related within 2 days after vaccination (day of vaccination and one subsequent day) and persisting continuously at Grade 3 for >72 hours
- **Unsolicited adverse events:**
  - The participant has any Grade 3 adverse event considered possibly, probably or definitely related to vaccination, persisting continuously at Grade 3 for >72 hours
  - The participant has an SAE considered possibly, probably or definitely related to vaccination
  - The participant has an acute allergic reaction or anaphylactic shock following the administration of vaccine investigational product

If the participant has an acute illness (moderate or severe illness with or without fever) or a fever (oral temperature > 37.5°C) at the scheduled time of administration of investigational product, the participant will not receive the vaccine at that time. The vaccine may be administered to that participant at a later date within the time window specified in the protocol or the participant may be withdrawn from the study at the discretion of the Investigator.

All vaccinated participants will be followed for safety until resolution or stabilisation (if determined to be chronic sequelae) of their SAEs.

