#### *5.8.2.3 Nivolumab Preparation and Administration*

Nivolumab will be prepared according to the Pharmacy Manual.

In Groups 3 and 4, the patients will be observed for 30 minutes after vaccination. If there are no safety concerns (vital signs and reactogenicity), nivolumab will be infused over 30 minutes and the patients will be observed in the study centre for a further 30 minutes post-infusion.

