#### 10.2.1 Analysis Sets

- The intent-to-treat set will consist of all participants who are randomised
- The safety analysis set will consist of all participants who received at least one vaccination (data will be summarised according to the vaccination actually received)
- The per-protocol analysis set will consist of all participants in the safety analysis set who received the correct study vaccine and who had no major protocol deviations
- The immunogenicity analysis set will consist of all participants in the per-protocol set and have available immunogenicity data to evaluate the immunogenicity endpoints and did not have any major protocol deviations that would impact on the results of the immunological analysis

Allocation of participants to the analysis sets (and whether any participant or specific data from a participant will be excluded) will be determined at the pre-database lock Data Review meeting.

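### SAP Table 2 moves Group 3 participants who get no second dose, or no nivolumab with it, to safety Group 2 for the whole study, and no adverse event table by randomised group is planned

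*SAP*

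**What the plan says.** Protocol 10.2.1 defines the safety set as everyone with at least one vaccination and adds that "data will be summarised according to the vaccination actually received". SAP 9.2.3 puts this into effect: "Participants will be presented according to the vaccination regimen actually received as defined in Table 2". SAP 12.7 uses the safety set for every safety analysis.

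The grouping rule is in SAP 10.1. For anyone given ChAdOx1-HBV without nivolumab on Day 0, the label depends on whether nivolumab was given at dose 2: "Group 2 = ChAdOx1-HBV in 1st vaccination, No Nivolumab in 2nd vaccination". Three rows of Table 2 matter here (randomised group, first product, second product, safety group):

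- "Group 3 ChAdOx1-HBV No vaccination given Group 2"
- "Group 3 ChAdOx1-HBV MVA-HBV (Nivolumab not given) Group 2"
- "Group 4 ChAdOx1-HBV + Nivolumab No vaccination given Group 4"

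The protocol gives two routes by which an AE can lead to the first two rows. Under 3.1.4, "Study participants who present with at least one of the following stopping rules will be withdrawn from further vaccination in the study". Under 5.8.2.3, nivolumab follows a 30-minute observation after vaccination: "If there are no safety concerns (vital signs and reactogenicity), nivolumab will be infused over 30 minutes".

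SAP 12.7.1.1 plans separate summaries of AEs, serious AEs and Grade 3 or greater AEs within 28 days of each vaccination. SAP 12.0 makes the population N the default denominator for percentages, and 12.7.1.1 names no other.

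**The concern.** Safety is the primary objective, and AEs within four weeks of dosing are a primary endpoint. Since protocol Version 6.0 only Groups 2 and 3 recruit, so this is the pair of groups planned at 16 each.

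Under Table 2, nobody is in safety Group 3 without having received nivolumab at dose 2. Safety Group 2 holds its own non-completers plus those of Group 3. Group membership therefore depends on what happens after baseline, including the AEs being counted. Three consequences follow.

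- A Group 3 participant whose AE prevents dose 2 is counted in Group 2, so the Group 3 count of such AEs is zero by construction.
- Groups 2 and 3 get the same treatment until Day 28, yet the first-vaccination tables can show a difference created only by the label.
- A mover without dose 2 is in the Group 2 denominator for the second-vaccination window without having had a second vaccination.

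SAP 12.7 plans no AE table by randomised group against which a reader could check this.

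**Working it through.** **The rows of Table 2.** There are 13. Eight keep the randomised group. Four move someone into Group 2 (two from Group 3, two from Group 4), one moves someone from Group 4 to Group 3, and none moves anyone out of Group 2. Among participants who had their full Day 0 treatment and no dose 2, those of Groups 1, 2 and 4 keep their group; only Group 3 changes.

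**The plan's own figure.** SAP 8.1 gives 16 participants an 80% chance of showing a severe or serious AE of 10% incidence. 1 − 0.9^16 = 0.815, so it reproduces. If a share f of such cases leads to dose 2 or its nivolumab not being given, the chance that the Group 3 table shows at least one case is 1 − (1 − 0.10(1 − f))^16. This is 81.5% at f = 0, 71.3% at 0.25, 56.0% at 0.5, 33.3% at 0.75 and 0% at 1. The documents give no value of f.

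**Worked counts.** The inputs are 16 randomised per group (protocol Table 1) and m movers from Group 3, so the safety N is 16 + m for Group 2 and 16 − m for Group 3. All event counts are assumptions.

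*First-vaccination window, dose 2 not given*

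| Assumption | By randomised group | Safety Group 2 | Safety Group 3 |
|---|---|---|---|
| No movers, no stopping AE | 0/16 each | 0/16 | 0/16 |
| One dose-2-stopping AE per group, m = 1 | 1/16 each (6.3%) | 2/17 (11.8%) | 0/15 |
| Two per group, m = 2 | 2/16 each (12.5%) | 4/18 (22.2%) | 0/14 |
| Grade 3+ in 2/16 each, m = 1, mover has one | 12.5% each | 3/17 (17.6%) | 1/15 (6.7%) |
| Any AE in 10/16 each, m = 1, mover has one | 62.5% each | 11/17 (64.7%) | 9/15 (60.0%) |
| Any AE in 10/16 each, m = 1, mover has none | 62.5% each | 10/17 (58.8%) | 10/15 (66.7%) |

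The direction depends on why dose 2 was missed: the last two rows point opposite ways.

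*Second-vaccination window, dose 2 not given.* Take one missed dose 2 per group and 5 participants with an AE among the 15 dosed in each. Group 2 then has N = 16 + 1 = 17, so the table shows 5/17 (29.4%) against 5/15 (33.3%). With dosed participants as the denominator, both groups are 5/15. Solicited AE tables have their own denominator (SAP 12.7.2.2) and are not diluted in this way.

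*Second-vaccination window, MVA-HBV given and nivolumab not given.* Take 5/16 in each group and m = 1. If the mover has an AE in the window, the result is 6/17 (35.3%) against 4/15 (26.7%). If not, it is 5/17 (29.4%) against 5/15 (33.3%).

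**Precision.** With one such AE, in Group 3 only, the randomised-group view is 1/16 (6.3%, exact 95% interval 0.2 to 30.2) against 0/16. The safety view is 0/15 in Group 3 (upper limit 21.8%) and 1/17 in Group 2 (5.9%, 0.1 to 28.7).

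**The case against.** The strongest defence is that Table 2 does what the protocol asks. Summaries by treatment received are prespecified, and a participant who never had nivolumab should not have AEs counted against it.

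For the row where MVA-HBV is given without nivolumab, this stands in full. The participant received the Group 2 regimen. A reader might infer that this row is a misassignment, or that it always makes Group 2 look worse. Neither follows: the row agrees with protocol 10.2.1, and its direction depends on whether the mover has an AE in the window.

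For the row without dose 2, it stands in part. A Group 2 and a Group 3 participant given only ChAdOx1-HBV have the same exposure, so one shared label is coherent. But ChAdOx1-HBV alone is neither group's regimen, so the as-received rule does not require that the label be Group 2, nor that the participant be counted in a second-vaccination denominator.

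A reader might also infer that any AE interrupting nivolumab leaves Group 3. The documents do not support that. A started infusion is still nivolumab at dose 2, so the participant appears to stay in Group 3, although Table 2 has no row for this.

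Nor are events hidden. They remain in the Total column (SAP 12.0) and the by-participant summaries (SAP 12.7.2.1), and the protocol requires narratives (10.2.2.6.1). Reasons for stopping the regimen are tabulated by randomised group (SAP 12.1), and the randomisation listing (SAP 12.3) links each case to its assigned group. Safety is descriptive, with no between-group test planned. The exposure table (SAP 12.5) is a weaker safeguard because it uses the same regrouped columns.

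**Conclusion.** The point holds as a reporting artefact that is cheap to remove. Certainty is high about the rule and low about its consequence. If nobody randomised to Group 3 missed dose 2 or its nivolumab, the two views coincide. If one or two did, assumed counts give gaps in the first-vaccination tables such as 2/17 against 0/15 or 3/17 against 1/15, where the randomised groups are equal. Those gaps are within the sampling uncertainty at this size, but they come from the label and not from treatment. The part needing correction is the row without dose 2, through both its first-vaccination numerators and its second-vaccination denominator. The nivolumab-not-given row needs only a supportive table.

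Two separate minor items do not bear on Table 2.

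- Protocol 8.2.4.3 records action taken with vaccine as none on the ground that a single dose is given. That conflicts with the two doses in protocol 5.2.1, the discontinuation summaries in protocol 10.2.2.6.1, and the withdrawal value used in SAP 12.7.2.1.
- SAP 10.9.1 imputes partial AE start dates against the first vaccination only. With dose 2 exactly on Day 28, an event with the day missing in the month of dose 2 falls in the dose-1 window unless dose 2 is on the first of a month, that is for 365 − 12 = 353 of 365 dose-1 dates. This is not an error rate: such an event may truly have begun before dose 2, and how often partial dates occur is unknown.

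**What to change.** 1. Add one supportive table of AEs and discontinuation AEs by randomised group, with a footnote identifying moved participants by study number.
2. Tabulate first-vaccination-window AEs by Day 0 regimen (Groups 2 and 3 pooled) or by randomised group.
3. Use participants given dose 2 as the denominator in the second-vaccination-window tables. Show AEs after Day 28 in participants not given dose 2 in a separate row or listing, so that they are not dropped.
4. State in Table 2 how a partial nivolumab infusion is classed.

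The cost is SAP wording, one or two more tables and minor reprogramming. The downside is that denominators will differ between the dose-1 and dose-2 tables.

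For the separate items, reconcile protocol 8.2.4.3 with protocol 5.2.1 and 10.2.2.6.1 and SAP 12.7.2.1. In SAP 10.9.1, add a rule for partial start dates in the month of dose 2. One option is to count the event in both windows, in which case it appears in both tables.
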